Approximately 400,000 colonoscopies are performed each year within the NHS for the investigation of gastrointestinal symptoms, including altered bowel habit, rectal bleeding and iron deficiency anaemia. Adenoma detection rate (ADR), defined as the number of procedures in which at least one adenoma is detected, is a widely accepted quality measure. A recent colonoscopy audit demonstrated an average polyp detection rate of 32.1%; however, ADR is variable between colonoscopists. A recent study estimated mean ADR of 15.9%. Patients found to have adenomas receive surveillance procedures, however these are currently based entirely upon number and size of adenomas with no patient factors considered. The NHS Bowel Cancer Screening Programme (BCSP)

invites all individuals aged 60-74 to undertake biennial faecal occult blood testing (FOBt). Screening is currently population based and non-targeted. Patients with a positive FOBt are invited for colonoscopy. The national Bowelscope screening programme is currently being rolled out in England and Wales, with the Lead applicants unit the first nationally to deliver this programme. All individuals aged 55 are invited for a single flexible sigmoidoscopy and adenoma clearance. Those deemed to be high risk undergo completion colonoscopy.

The mean ADR per colonoscopist within the FOBt BCSP is 46.5%, which is much higher than the symptomatic population due to the targeted nature of the programme. The BCSP has demonstrated a significant stage shift in CRC diagnosed. At present, the FOBt based screening programme is not providing protection against right sided CRC. A trial within the Scottish screening programme demonstrated that screening was an effective environment for interventions to alter patient behaviour.

In summary, although a study in an Asian population suggested an association between NAFLD and colorectal neoplasia, this has not been repeated in a Western population. It is important that the association is explored in a Western population but using non-invasive markers of liver disease and a wider range of colorectal neoplasia risk factors. This will allow development of a model to predict colorectal adenoma risk guiding screening and surveillance.

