#### 3. Study Design

A multi-centre observational study will identify colorectal neoplasia burden in patients undergoing index screening or diagnostic colonoscopy. Non-invasive markers of liver disease and obesity will be assessed and a multivariate model constructed. The primary outcome is to develop a risk model with emphasis on obesity-related factors, particularly in the population with abnormal liver enzymes, to inform colorectal screening. Secondary outcomes will support this model by identifying demographics which contribute to increased predisposition to colorectal neoplasia, additionally assessing whether the presence/degree of liver fibrosis affects this risk. The link between NAFLD, obesity and colorectal neoplasia in terms of adenoma burden, site and histological features will also be explored.

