#### 3.1 Patient Recruitment

Eight Northern Regional Endoscopy Group (NREG- with a strong track record in delivering large endoscopy trials) units and Kettering General Hospital NHS Trust will recruit patients. Sites from NREG include: South Tyneside District Hospital, Freeman Hospital, Northumbria NHS Trust, Sunderland Royal Hospital, James Cook University Hospital, County Durham and Darlington Foundation Trust, Leeds Teaching Hospitals NHS Trust and North Tees University Hospitals.

Approximately 1430 patients undergoing colonoscopy as part of the BCSP or symptomatic service (most commonly patients with iron deficiency anaemia, altered bowel habit, weight loss and rectal bleeding) will be identified from endoscopy lists and recruited by a member of the research team. The final target number of participants will be refined after the first 100 participants have been recruited however this is not expected to vary significantly. Methodology by Peduzzi et al is used to calculate the minimum number of cases required to measure all variables and develop the risk model. Sample size N=10\*(k/p), where k is the number of covariates to be investigated in the model (n=15) and p the smallest of the proportions of positive or negative cases (=ADR=0.15). For non-BCSP population, ADR is around 15%; 1000 from this population are required. Minimum ADR within the BCSP is 35%; 430 cases are required to adequately power and build the model. This will allow resolution of small scale effects of covariates on risk prediction. Using Demidenko's method, the sample size needed for logistic regression with 80% power and 5% level of significance is N=8V/β2, where  $\beta$  is the natural log of the

odds ratio and V is logistic model variance due to covariates. This formula can be rearranged to determine the minimum odds ratio that can be detected at a sample size of 2000 with sufficient power. Assuming a moderate standard error in the regression (se=0.125), and calculating V from the standard error (V=(se\*vN)2) the study will have sufficient statistical power to detect an effect with a small effect size with an odds ratio of 1.42. The final sample size will be refined using data from the first 100 participants and observed effect size(s), however, the total number of recruits will not exceed 2000.

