#### 6. Statistics and Data Analysis

Data from the CRFs will be transferred to a secure and encrypted electronic computer database. Statistical analysis will be undertaken by [name], Professor of Biological Modelling at Newcastle University.

The relationship between adenoma incidence, NAFLD and blood markers will be investigated using logistic regression whilst adjusting for patient-related demographic variables including age and gender. This will assess the independent contribution of predictors to the odds of adenomas being found. Stepwise removal of non-significant covariates will then be used to identify variables best able to predict adenoma presence. ROC plot and AUC analyses of sensitivity and specificity will be used to characterise the ability of the model to discriminate between patients with and without adenomas and their potential as a predictive tool. These analyses assess the independent contribution of variables to the probability that adenomas will be found, but do not allow for confounding, interaction and associated indirect effects on detection. Structural Equation Modelling (SEM) will be used to investigate impact of indirect and direct effects of the predictors on adenoma incidence. Parsimonious models for logistic regression and SEM will be compared in terms of their ability to predict adenoma presence.

As multiple adenomas may occur, the extent to which adenoma number is related to abnormal liver enzymes using Poisson regression models and SEM will be measured, following the same analytical framework. It is anticipated that the presence of multiple adenomas will be zero-inflated, with some patients having zero and others many. The extent to which zero-inflated models (eg allowing for aggregation) improve the prediction of adenomas will be assessed. Robustness and validation of all models will be validated using bootstrapping. The best model will be developed into a predictive tool.

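### Bootstrapping is the only validation named before the model becomes a screening tool; if patients are resampled, it does not show whether predicted risks hold at a unit that contributed no data

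*Protocol*

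**What the plan says.** Protocol section 6 states that "Robustness and validation of all models will be validated using bootstrapping", and then that "The best model will be developed into a predictive tool". Nothing lies between the two steps. The only performance analysis named is discrimination: "ROC plot and AUC analyses of sensitivity and specificity will be used to characterise the ability of the model to discriminate". The section names no calibration measure, held-out unit or external sample. The adjustment variables it mentions are patient-level, and it does not say whether the bootstrap resamples patients or units.

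Section 3 makes a risk model the primary outcome, "particularly in the population with abnormal liver enzymes, to inform colorectal screening". Section 3.1 lists the recruiting organisations: "Eight Northern Regional Endoscopy Group (NREG- with a strong track record in delivering large endoscopy trials) units and Kettering General Hospital NHS Trust", nine in all. Section 1 remarks of the adenoma detection rate: "however, ADR is variable between colonoscopists".

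**The concern.** The outcome modelled is an adenoma being found, which depends partly on who performs the colonoscopy and where. A bootstrap that redraws patients from the pooled data recreates the same mix of units each time. It measures how far the model is tuned to this sample of patients. It cannot measure how far the model's risks are tuned to these particular units.

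A tool that informs screening will be applied at other units, where its absolute risks need to be roughly right. If only the bootstrap is reported, the results would look much the same whether the nine organisations are alike or quite different. The study would then close without evidence on a question its own data could partly answer.

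**Working it through.** **The plan's own figures.** These reproduce and are not in dispute.
- Sample size, N = 10k/p with k = 15: 10 × 15/0.15 = 1000 and 10 × 15/0.35 = 428.6, total 1428.6 against the stated 1430.
- Detectable odds ratio, exp(√(8V/N)) with V = (0.125√N)²: N cancels, giving exp(0.125√8) = 1.42, as stated.

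**Inputs for the check**
- From section 3.1: N = 1430, 15 covariates, nine organisations, adenoma rates of 15% (1000 patients) and 35% (430 patients).
- Expected events: 1000 × 0.15 + 430 × 0.35 = 300.5, an overall rate of 300.5/1430 = 0.210.
- Assumed: the between-unit SD of the log-odds, varied from 0 to 0.7, because the protocol gives none.

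**Simulation.** For each SD there were 60 simulated studies, each with patients spread at random over nine units. A logistic model with the 15 covariates and a screening-programme indicator was fitted. There were 40 patient-level bootstrap resamples per study, and the model was then applied to five new units per study. Stepwise selection was not simulated. Units differed in the intercept only. The measures were:
- optimism-corrected AUC: apparent AUC minus the mean, over resamples, of the AUC in the resample minus the AUC in the full data;
- calibration slope: the coefficient of the linear predictor in a logistic refit;
- calibration-in-the-large: the intercept with the linear predictor as offset;
- observed/expected (O/E): observed rate divided by mean predicted risk.

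| Assumed SD | Bootstrap AUC | Bootstrap slope | Bootstrap calibration-in-the-large | New-unit O/E, central 95% | New units with O/E below 0.80 or above 1.25 | Leave-one-unit-out: SD of calibration-in-the-large |
|---|---|---|---|---|---|---|
| 0 | 0.712 | 0.901 | 0.001 | 0.87-1.13 | 1% | 0.21 |
| 0.2 | 0.712 | 0.901 | 0.001 | 0.72-1.36 | 17% | 0.29 |
| 0.3 | 0.713 | 0.903 | 0.001 | 0.59-1.50 | 34% | 0.38 |
| 0.5 | 0.713 | 0.903 | 0.001 | 0.43-1.92 | 53% | 0.55 |
| 0.7 | 0.701 | 0.895 | 0.001 | 0.27-2.13 | 64% | 0.75 |

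The bootstrap columns hardly change and the new-unit columns do. Mean AUC at a new unit stayed at 0.711 to 0.713 throughout. With intercept differences only, the ranking of patients within a unit survives, and it is the absolute risks that shift.

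**Hand check.** logit(0.210) = −1.324. At SD 0.3, a unit at ±1.96 × 0.3 = ±0.588 has a rate of 0.129 or 0.324, so O/E is 0.61 or 1.54. At SD 0.5 (±0.98) the rates are 0.091 and 0.415, so O/E is 0.43 or 1.97. Both agree with the table.

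**What leaving organisations out can show.** With equal recruitment each organisation has 1430/9 ≈ 159 patients and 300.5/9 ≈ 33 events. The standard error of calibration-in-the-large at one site is about 1/√(159 × 0.21 × 0.79) = 0.19, close to the 0.21 seen with no heterogeneity. With nine sites (8 df, normal approximation), a true SD of 0.21 gives sample SDs from 0.21√(2.18/8) = 0.11 to 0.21√(17.53/8) = 0.31. At an assumed between-unit SD of 0.2 the held-out SD averages 0.29, so it exceeds 0.31 only when χ²₈ > 8 × (0.31/0.29)² = 9.1, about one time in three. Larger heterogeneity is easier to see.

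A second simulation, with its own parameter choices, gave average lowest and highest held-out O/E across the nine sites of 0.75 to 1.27 (SD 0, noise only), 0.61 to 1.50 (SD 0.3) and 0.48 to 1.83 (SD 0.5).

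**The case against.** Bootstrapping is a sound internal validation, and the protocol never says that it demonstrates performance at new units. It speaks of informing screening and plans publication and presentation, with no deployment step. Calibration measures and site-wise checks could properly sit in an SAP that is not shown. All of this stands, and it makes the point an improvement to a stated method rather than an error in it.

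Three stronger readings are tempting, and the documents support none of them.
- A reader might infer that the bootstrap must be blind to differences between units. That is true of a patient-level bootstrap, but the resampling unit is not stated. Resampling whole units would reflect some variation, though only among the same nine.
- A reader might infer that the model will miscalibrate badly elsewhere. The protocol gives no between-unit SD. Its remark in section 1 concerns colonoscopists, and a unit's rate averages over its colonoscopists, so units may differ less. With no between-unit variation there is no harm.
- A reader might take a bootstrap O/E near 1.00, or calibration-in-the-large near zero, as telling evidence. It is almost automatic, because a logistic model with an intercept reproduces its own event total. The informative contrast is that bootstrap AUC and slope stay flat while new-unit calibration spreads.

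The remedy also has limits. It uses the same nine organisations, eight of them from one regional group, and it is weak against modest heterogeneity.

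**Conclusion.** The point holds in a conditional form. Bootstrapping is the only validation the protocol names before the tool is built. If patients are resampled, it leaves performance at a non-contributing unit untested. The size depends on an assumed quantity: new-unit O/E of about 0.87-1.13 with no between-unit variation, 0.59-1.50 at an SD of 0.3 and 0.43-1.92 at 0.5. These ranges also rest on intercept-only differences, equal expected recruitment and no stepwise selection. This is a low-cost improvement that changes what the study can say about use elsewhere. It does not invalidate the planned analysis.

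**What to change.** In section 6:
1. Keep bootstrapping, describe it as internal validation for overfitting, and state the resampling unit.
2. Add leave-one-organisation-out (internal-external) validation over the nine recruiting organisations, repeating the whole model-building procedure, including the stepwise removal of covariates, each time.
3. Report held-out AUC, calibration slope and O/E, pooled by random-effects meta-analysis with a prediction interval. Do not interpret single-site results.
4. Limit any statement about use at other units to what that interval supports, and say that external validation is still needed.

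The cost is analysis time only, with no extra patients, visits or data. The prediction interval is likely to be wide, and modest heterogeneity may go undetected.

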#### 7. Regulatory Issues

#### 7.1 Ethics approval

Ethical approval will be sought via the NHS Research Ethics Committee (REC) prior to study commencement. As the majority of patients undergoing colonoscopy have an intravenous cannula inserted for sedative medication or smooth muscle relaxants, the necessary blood tests can be obtained from this. To prevent haemolysis, a slightly larger cannula will be used (18G). In some cases,

the larger cannula may cause slightly more discomfort than the smaller cannulae commonly used for this procedure.

Patients will be informed of the risks associated with standard colonoscopy and consented for the procedures according to standard practice, in addition to a study specific consent form which will be explained by the research team.

The study will be conducted in accordance with the recommendations for physicians involved in research on human subjects adopted by the 18th World Medical Assembly, Helsinki 1964 and later revisions.

#### 7.2 Consent

Consent to enter the study will be sought from each participant only after a full explanation has been given, an information leaflet has been offered and time allowed for consideration. Signed participant consent will be obtained. The right of the participant to refuse to participate without giving reasons will be respected. All participants will be informed of their right to withdraw at any time from the study without giving reasons and without prejudicing further treatment. Potential participants will be assessed by a member of the study team, eligibility will be confirmed and baseline assessments performed.

#### 7.3 Confidentiality

The Caldicott Principles and Data Protection Act will be fully adhered to when dealing with patient identifiable data. The Chief Investigators will preserve the confidentiality of participants taking part in the study. No staff beyond the usual care team will have access to identifiable data. No identifiable participant data will be passed outwith the participating Trusts. The data will be held at the site in accordance with local Trust policies and will be destroyed following the study close in accordance with local Research and Development protocols.

#### 7.4 Sponsor

South Tyneside Foundation Trust will be the sponsor for this trial.

#### 7.5 Funding

This study will be conducted on existing NHS and BCSP lists, at no extra cost to the NHS. Funding for cannulation and blood collection equipment, blood test analysis and clinical trial unit costs will be provided by Norgine Pharmaceuticals.

The chief investigator is a full-time dedicated clinical researcher and will be supported by a research team consisting of a research fellow and research nurses, who will invite, assess and consent participant, in addition to collecting data. No additional NHS resources will be required to conduct this study.

#### 8. Study Management

#### 8.1 Data Protection

Patient data will be held on site at the Trust in accordance with local Trust policies. Patients will be assigned a unique study ID at study entry. All data passed to the trial team will have all patient identifiable data removed, aside from the unique study ID. Patients who withdraw will have all data collected up until the point of withdrawal included in the study. This data will be uploaded onto an electronic CRF and included in the analysis of the study. Data will be submitted either directly onto the electronic CRF or onto paper CRF before input into the electronic CRF.

#### 8.2 Records Retention

The Principal Investigator will retain all study related records (CRFs, source documents, Investigator site file) for fifteen years after the end of the study. All study related records may be archived after the study has closed, the database has been locked and notification has been received from the trial team. The PI will be responsible for ensuring that these archived records are accessible, as required by current legislative regulations. Archiving will occur at each site according to local R+D protocols.

#### **8.3 Protocol Compliance**

A representative group of staff who will be part of the research team will attend a site initiation meeting to ensure compliance with the protocol and allow training in study procedures and data collection methods. The PI at each study site will apply for local R+D approval. The PI will sign a copy of the ethically approved protocol to confirm agreement to carry out all study related tasks in accordance with the protocol.

#### 8.4 Responsibilities

All staff involved in the study will undergo GCP training. Day to day delivery will be supported by a research nurse and a research fellow. The responsibilities of the trial team are as outlined below.

#### Chief Investigator:

- 1. Protocol development
- 2. Coordination of trial
- 3. Education of trial team
- 4. Ensuring GCP training and governance
- 5. Support application through approval processes and ethics
- 6. Data interpretation
- 7. Contribution to report and papers for publication
- 8. Ensure uploading of accrual data

#### Principal Investigators

- 1. Protocol development
- 2. Coordination of trial
- 3. Education of trial team, hosting of trial
- 4. Ensuring GCP training and governance
- 5. Support application through approval processes and ethics
- 6. Data interpretation (including timely assessment of seriousness of adverse events)
- 7. Contribution to production of report and papers for publication
- 8. Ensure uploading of accrual data
- 9. Overall responsibility for conduct and running of the trial at site
- 10. Ensuring local governance
- 11. Applying for R&D approval at their site
- 12. Recruitment and study conduct according to protocol

#### 9. Financing and Insurance

This study will be funded by the Norgine Pharmaceuticals. Standard NHS indemnity arrangements are in place.

#### 10. Dissemination

OSCAR is supported by the British Society of Gastroenterology (BSG) Endoscopy Research Committee (Appendix 2). The study has been reviewed and endorsed by the Bowel Cancer Screening Research Committee (Appendix 3).

Statistical analysis will be undertaken by [name], and the results will be written up in the form of a report by the research and academic team. Data from the study will be disseminated to participating patients within the study via the Trust's websites. The results will then be submitted for publication in international peer reviewed journals and presented to the British Society of Gastroenterology Endoscopy Research Committee, BSG guideline groups and the Bowel Cancer Screening Programme. Feedback will be given to regional and national Endoscopy leads, maximising the exposure of findings to colonoscopists. Data will also be disseminated to local networks, and national and international symposia.

#### **11. Publication Policy**

The chief investigators will take responsibility to present and publish the outcomes of the study. The results will be disseminated through peer reviewed national/international journals and learned scientific societies.

#### Appendix 4- OSCAR study Gaant chart

	2015								2016											2018										91 02 91 02										2020	
	Aug	Sept	ti Ott	Nov	Dec Jan-Dec	lan	Feb	Mar	Apr	June	P	Aug	Sept	t N	Dec	lan	Feb	Mar	Apr Mav	June	P	Aug	Sept Oct	Nov	Dec	Jan	Feb	Mar Apr	May	June	P	Aug	Sept Oct	Nov	Dec	Jan	Feb				
Literature review																																									
Protocol development																																									
Completion of IRAS																																									
Ethics process																																									
Local R&D																																									
Site initiations																																									
Identify participants																																									
Patient invitation																																									
Patient recruitment																																									
Data collection																																									
Site initiation and monitoring visitis																																									
Review of final study size																																									
Data analysis																																									
Risk model creation																																									
Write up of study results																																									
Results dissemination
